4.2 INCLUSION & EXCLUSION CRITERIA

Inclusion criteria:

- Adult patients aged ≥ 18 years
- Patients can be newly presenting to or existing users of the specialist service in question (eg podiatry, vascular surgery)
- Patients with recurrent wounds, including multiple wounds, are eligible; largest ulcer to be index wound
- If infection occurs and antibiotics applied, whilst in study, then this is not deemed an exclusion criterion.
- Prophylactic systemic antibiotic use is not an exclusion criterion
- Chronicity: clinical diagnosis of ulcer with wound duration > 30 days.
- Wound type:
 - Leg ulcer (can be venous, mixed or arterial in nature)
 - o Foot ulcer (can be diabetic or non-diabetic in nature)

Exclusion criteria:

- Aged < 18 years
- Any reasons for the patient being unable to follow the protocol, including lack of mental capacity to consent to taking part in the study.
- The patient has concurrent (medical) conditions that in the opinion of the investigator may compromise patient safety or study objectives
- Confirmed and ongoing wound infection at baseline which is already being treated with systemic antibiotics.
- Previous participation in BIOME study

5 STUDY PROCEDURES

5.1 INFORMED CONSENT

Before being recruited to the clinical evaluation, the patient must have consented to participate, after the nature, scope and possible consequences of the evaluation have been explained in an understandable form. A patient information leaflet and informed consent form will be provided to the patient. Consent to take part in this research is obtained from adult patients, where they possess mental capacity.

During the consent procedure the following information will be outlined in writing, which will also be relayed verbally: a) The evaluation involves research, a description of the aims of the evaluation and how it will be organised and the expected duration of the patient's participation; b) Any negative effects possibly attributable to the novel infection detection test kit; c) The freedom to ask for further information, and to withdraw from the study, at any time; d) The extent, if any, to which confidentiality of records identifying the patients will be maintained and that the Regulatory Authorities may inspect the records.

Although the clinical staff will be trained in obtaining informed consent as part of professional development, members of staff involved in the consent process will be encouraged to have current ICH Good Clinical Practice training.

5.2 STUDY PROCEDURES

Initial assessments at visit 1 (week 0)

After completing informed consent, the nature of the patient's wound will be recorded as well as the other relevant clinical parameters and demographics. The first WOUNDCHEK™ test will also be conducted. See Table 3 for an overview. Dressing selection, dressing frequency and all other aspects of their wound care will continue to be the responsibility of the clinical team – however, if they are influenced in this decision by the result of the WOUNDCHEK™ test then they are asked to record this in the clinical report form.

All visit assessments

Study visits will coincide with standard clinic attendance by patients. At the study visits week0 and week6, a diagnostic swab using the WOUNDCHEK™ infection detection test kit is performed in accordance with the SOP in Appendix 5.

The clinical staff treating the patient will ascertain their opinion regarding infection status of the wound prior to completing the WOUNDCHEK™ detection test, and will therefore be blinded to at least the first result of using the kit. Where possible, a member of the research team plus the clinical assessor will assess result of the WOUNDCHEK™ test.

Table 4, Overview of study activities per time point for different study participants.

Weeks	Visit 1 (wk 0)	Visit 2 (wk 6)#	Visit 3 (wk 12)#
Treatment deviation question	X	Χ	
WOUNDCHEK™ test (method, see appendix 6)	Χ	Χ	
Wound healed status~	n/a	X (if healed, no other	X (if healed, no other
		outcome measures)	outcome measures)
Clinical opinion of ulcer re. infection	Χ	Χ	Χ
PUSH score ulcer size (appendix 3)	X	Χ	Χ
VAS pain scale (appendix 3)	Χ	Χ	Χ
SINBAD score (foot ulcers only, appendix 4)	X	Χ	X
QoL EQ-5D-5L (appendix 5)	Χ	Χ	Χ
Wound measurement*(if standard care	X	Χ	Х
activity)			

[~]Wound status (healed vs non-healed), definition is: complete epithelial cover in the absence of a scab (eschar) with no dressing required bar any protective dressing. There is no minimum length of time that the index site has to have been in said condition for when participant present for follow-up study visit. # Can be \pm two weeks.

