5.3 DEFINITION OF END OF STUDY

The end of trial is the date of the last assessment in relation to the study or wound closure, whichever occurs first. If a wound is healed and any follow-up visit(s) were to take place thereafter, then these do not have to take place.

^{*}Using 'Minuteful for Wound' application (by Healthy.io), wound tracing sheet, or ruler measurement; needs to be consistency in method between different visits.

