varicose veins, atrial fibrillation, history of deep venous thrombosis, heart failure. Moderate-severe comorbidities will be history of myocardial infarction, stroke or transient ischaemic attack, CKD stage 4 or higher, peripheral vascular disease, history of amputation. Any other significant non-vascular conditions will be recorded too (e.g. COPD, cancer, auto-immune disease).

Treatment Deviation outcome data will be collated and presented with descriptive statistics. This will be in the form of the number of treatment deviations that occurred as a result of the WOUNDCHECK test result, the nature of the deviation and the longer term patient/wound outcomes at week 6 and/or week 12.

Ulcer healing and more general health measures is assessed by the following parameters:

- Ulcer status (healed vs non-healed)
- Ulcer size (cm²)
- PUSH score
- SINBAD score
- Visual analogue pain score
- EQ-5D-5L

To assess the Ulcer size, PUSH score, visual analogue pain score, which are measured every 6 weeks, the average difference between groups (ie negative or positive Woundchek test outcome) will be calculated and Mann-Whitney U-test will be applied.

To measure patient-reported outcome measures on quality of life (EQ-5D-5L) at baseline, week6 and week 12; the the Mann-Whitney U-test will be performed between Woundchek test outcome groups.

Analysis will be performed on a per protocol basis, and inferential statistics will be performed on pooled data. Data will first be collated in Microsoft Excel, followed by analyses performed using SPSS v24.

9 Data handling and Monitoring

Data arising from this study is confidential. Identifiable information can only be accessed by delegated members of the study team. Anyone in the research team who will work on Trust premises and see patients, and does not have a substantive contract with NCIC, will need to apply for a letter of access via the NIHR research passport scheme.

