Appendix 2, Study participant flowchart

Appendix 3, PUSH score and VAS pain scale

The Pressure Ulcer Scale for Healing (PUSH) tool is a standardised method of assessing and monitoring the severity and healing of both pressure ulcers and venous leg ulcers (Stotts et al, 2001; Ratliff & Rodeheaver 2005). The Pressure Ulcer Scale for Healing (PUSH) is a valid, responsive, evaluative tool to monitor and document wound progress of foot ulcers (Hon, 2010).

Pressure Ulcer Scale for Healing (PUSH) PUSH Tool 3.0

[figure not shown]
Patient Name	Patient ID#	
Ulcer Location	Date	

Directions:

Observe and measure the pressure ulcer. Categorize the ulcer with respect to surface area, exudate, and type of wound tissue. Record a sub-score for each of these ulcer characteristics. Add the sub-scores to obtain the total score. A comparison of total scores measured over time provides an indication of the improvement or deterioration in pressure ulcer healing.

LENGTH	0	1	2	3	4	5	Sub-score
X	0	< 0.3	0.3 – 0.6	0.7 – 1.0	1.1 – 2.0	2.1 – 3.0	
		6	7	8	9	10	
(in cm²)		3.1 – 4.0	4.1 – 8.0	8.1 – 12.0	12.1 - 24.0	> 24.0	
EXUDATE	0	1	2	3			Sub-score
AMOUNT	None	Light	Moderate	Heavy			
TISSUE	0	1	2	3	4		Sub-score
TYPE	Closed	Epithelial Tissue	Granulation Tissue	Slough	Necrotic Tissue		
			1				TOTAL SCORE

Visual analogue pain scale, for pain currently experienced from site of wound (enter in table, not on the scale itself):

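### Ulcer size in cm² is analysed as if measured every 6 weeks, but Table 4 measures it only where standard care does, by any of three methods not harmonised between patients

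*Protocol*

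**What the plan says.** Section 8.4 lists ulcer size in cm² and the PUSH score as separate parameters. It describes the timing without any condition: "To assess the Ulcer size, PUSH score, visual analogue pain score, which are measured every 6 weeks". The planned analysis is between patients: "the average difference between groups (ie negative or positive Woundchek test outcome) will be calculated and Mann-Whitney U-test will be applied".

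Table 4 in Section 5.2 has two size rows. The PUSH row is marked at weeks 0, 6 and 12 with no condition. The direct measurement row is marked at the same visits but begins "Wound measurement*(if standard care" and ends with the word activity, so it applies only where the clinic measures routinely. The Table 4 footnote, printed under Section 5.3, permits the "application (by Healthy.io), wound tracing sheet, or ruler measurement" and adds that there "needs to be consistency in method between different visits".

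The PUSH form in Appendix 3 instructs the assessor: "Observe and measure the pressure ulcer. Categorize the ulcer with respect to surface area, exudate, and type of wound tissue". Its size item is length x width in cm², scored 0 to 10 in bands, with an open top band above 24.0 cm².

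The regression list in Section 8.4 includes the size of the wound without unit or instrument. The same section treats the PUSH score as part of wound size when describing the baseline table, and Section 8.1 collates baseline size from the CRF or patient records.

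**The concern.** The schedule and the analysis disagree about a named outcome. One section says ulcer size is measured every 6 weeks; the table that governs data collection says it is measured if the clinic would have done so anyway. Staff following Table 4 will not necessarily produce the data that Section 8.4 analyses.

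The method rule also protects the wrong contrast. Keeping one method between visits supports change within a patient, whereas the planned Mann-Whitney test compares different patients. Recruitment runs across podiatry, vascular and tissue viability clinics (Section 4.1), which may differ both in how they measure and in the ulcers they see. If they do, part of a size difference by WOUNDCHEK result could reflect clinic or method.

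This cannot be repaired at the analysis stage. An analysis plan cannot recover an area that was never measured, and can allow for method only if method was recorded. The part of the CRF that can be read (Appendix 1) shows a yes/no box for PUSH completion but no cm² field and no method field. Some of that form is missing from the text available, so this is supporting evidence only.

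**Working it through.** The protocol gives no figure for this point, so the check is mainly a comparison of passages.

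**Passages side by side**

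| Item | Table 4 and footnote | Section 8.4 |
|---|---|---|
| Ulcer size in cm² | weeks 0, 6, 12, only if part of standard care | every 6 weeks, no condition |
| Method | app, tracing sheet or ruler | not stated |
| Consistency | between visits | comparison is between patient groups |
| PUSH, including its size item | weeks 0, 6, 12, no condition | every 6 weeks |
| Size covariate | – | wound size, no unit or instrument |

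The first row is a contradiction. The second and third leave a gap: nothing aligns the method between patients or clinics. The fourth shows that an unconditional size observation already exists.

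**How far two methods could differ (illustration only)**

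Assume an elliptical ulcer, and a ruler user who reports the raw product of length and width.
- Traced area = (π/4) × L × W, so ruler product / traced area = 4/π = 1.273.
- A traced area of 3.1 cm² would read 3.1 × 1.273 = 3.95 cm² by ruler, about 27% larger.
- Both values lie in the same PUSH band (3.1–4.0, score 6).

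The footnote does not say how a ruler reading becomes an area, and this calculation does not cover the app.

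**What the regressions would lose (conditional)**

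This applies only if cm² is the size covariate and incomplete records are dropped. The protocol states neither.
- The plan's rule is N = 10k/p. Its stated 250 samples follow from k = 5 and p = 0.20: 10 × 5 / 0.20 = 250. (The 0.16 printed beside it gives 312.5, which is a separate matter.)
- Planned samples are 258, and 1 − 250/258 = 3.1%. Missing size data above 3.1% would take 258 below 250. The 234 samples required without attrition are already below 250, so this margin should not be read as a threshold created by size measurement.
- Missingness is not given. Assuming 10%, 25% or 50% of the 234 samples lack a cm² value, 210.6, 175.5 or 117 remain. At p = 0.20 these support N × 0.20 / 10 = 4.2, 3.5 or 2.3 covariates, against 4.7 with none missing.

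If the PUSH size item is the covariate, the loss from conditional measurement is nil.

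**The case against.** The strongest reply is that little hangs on the cm² outcome. No stated objective concerns healing or change in area; size enters the objectives only as a candidate factor, and PUSH supplies that at every visit. The exact form of a covariate and the handling of missing data are commonly left to an analysis plan. The study has one centre, and relying on routine measurement suits a design in which wound care stays with the usual team. A method difference distorts the group comparison only if method tracks the WOUNDCHEK result; otherwise it adds noise to a rank test on a quantity that spans PUSH bands from below 0.3 to above 24 cm².

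Much of this stands, and it rules out three stronger readings.
- A reader might infer that the regressions will lose samples. The text does not say that cm² is the covariate.
- A reader might infer that cm² is selectively missing and not comparable between patients. No passage says which clinics measure, how often or by which method. These are risks, not established facts.
- A reader might take 27% as the bias. It rests on an assumed shape and an assumed use of the ruler, and nothing ties method to test result.

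The reply does not remove the contradiction. Section 8.4 chose to name cm² separately from PUSH, state its frequency and specify a test for it. Whether it is measured, and how, is a matter for the protocol's schedule.

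**Conclusion.** The point holds in limited form. Sections 5.2 and 8.4 conflict on whether ulcer size in cm² is collected at each visit, and the permitted methods are not harmonised between the patients being compared. Followed as written, the plan secures neither complete nor harmonised data for this outcome. The size of the problem cannot be stated, because missingness and the mix of methods are unknown; the figures above are illustrations under stated assumptions.

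The primary chi-squared test and kappa do not use ulcer size and are untouched. The effect on the regressions depends on which size variable is used. That choice is worth fixing in the text, since Section 2.1 ranks the search for characteristics behind non-matching results as the primary objective, while the summary ranks it as secondary. The reading of the footnote, that its consistency rule concerns visits and not patients or clinics, follows its wording.

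**What to change.** Reconcile Table 4 with Section 8.4:

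1. At weeks 0, 6 and 12, for ulcers not healed, record on the CRF the length and width in cm already needed for the PUSH size item. Remove the standard-care condition for this measurement.
2. In Section 8.4, define ulcer size in cm² as that product, and name the same variable as the wound-size covariate in the regressions.
3. Where an app or tracing area is also taken in routine care, keep it as a supplementary measure and record the method.

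The cost is two numeric CRF fields and short edits to Table 4 and Section 8.4. No procedure is added, because PUSH is already due at all three visits. The drawback is that length x width overstates the area of non-rectangular ulcers by an amount that varies with shape. That overstatement is not guaranteed to be equal in the WOUNDCHEK-positive and -negative groups, so the report should describe the variable as a length x width product, not as a true area.

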5.3 DEFINITION OF END OF STUDY

The end of trial is the date of the last assessment in relation to the study or wound closure, whichever occurs first. If a wound is healed and any follow-up visit(s) were to take place thereafter, then these do not have to take place.

^{*}Using 'Minuteful for Wound' application (by Healthy.io), wound tracing sheet, or ruler measurement; needs to be consistency in method between different visits.

5.4 DISCONTINUATION OR WITHDRAWAL OF PARTICIPANTS

Each participant has the right to withdraw from the study at any time – withdrawal of patients has been anticipated in the sample size calculation. In addition, the Investigator may discontinue a participant from the trial at any time if the Investigator considers it necessary for any reason including:

- Ineligibility (either arising during the trial or retrospectively having been overlooked at screening)
- Significant protocol deviation/violation
- An adverse event which requires discontinuation due to inability to continue to comply with trial procedures (eg hospitalisation, death)
- Any event which results in inability to continue to comply with trial procedures
- Withdrawal of Consent
- Loss to follow-up

Data already collated as part of the study will be retained if a subject withdraws from the study.

5.5 SOURCE DATA

Source data will include patient's hospital records (for wound type and classification of infected wounds) and the Case Record Form for the results of the novel infection detection test. WOUNDCHEK™ will have no access to patient data other than pseudo-anonymised data for the test results and associated medical opinion for the relevant wounds.

All documents will be stored safely in confidential conditions. On all study-specific documents, other than the signed consent, the participant will be referred to by the study number.

6 EVALUATION PRODUCT

6.1 DESCRIPTION OF WOUNDCHEK™ LIMITED DETECTION KIT

The WOUNDCHEK™ infection detection test kit is CE-marked. WOUNDCHEK™ Bacterial Status is able to detect EPA (elevated protease activity). WOUNDCHEK™ Bacterial Status will help clinicians establish within minutes which wounds may most benefit from a protease modulating therapy, ensuring appropriate and targeted use of these therapies.

6.2 DISTRIBUTION & ACCOUNTABILITY

Delivery of kits to the centre will be arranged by WOUNDCHEK™ Limited. Records will be retained for kits received and on which dates.

7 SAFETY

7.1 SAFETY DEFINITIONS

Table 5, Description of different adverse event reporting definitions.

Adverse Event (AE)	Any untoward medical occurrence in a patient or other clinical investigation
Adverse Everit (AL)	participant taking part in a trial of a medical device, which does not

necessarily have to have a causal relationship with the device under investigation.

An AE can therefore be any unfavourable and unintended sign (including an abnormal laboratory finding), symptom or disease temporally associated with the use of the device, whether or not considered related to the device.

Serious Adverse Event

A serious adverse event is any untoward medical occurrence that:

- results in death
- is life-threatening
- requires inpatient hospitalisation or prolongation of existing hospitalisation
- results in persistent or significant disability/incapacity
- consists of a congenital anomaly or birth defect.

Other 'important medical events' may also be considered serious if they jeopardise the participant or require an intervention to prevent one of the above consequences.

NOTE: The term "life-threatening" in the definition of "serious" refers to an event in which the participant was at risk of death at the time of the event; it does not refer to an event which hypothetically might have caused death if it were more severe.

7.2 PROCEDURES FOR RECORDING ADVERSE EVENTS

All SAEs need to be reported to the sponsor/host Trust R&D **within one working day** of the investigator team becoming aware of them. WOUNDCHEK™ will be updated on any SAE incidences once every two months or 20 recruited patients (whichever occurs sooner)

The only device to be in contact with the patient is the sterile swab provided by the hospital and employed by hospital staff only.

7.3 CAUSALITY

The relationship of each adverse event to the trial must be determined by a medically qualified individual according to the following definitions:

Related: The adverse event follows a reasonable temporal sequence from swabbing. It cannot reasonably be attributed to any other cause.

Not Related: The adverse event is probably produced by the participant's clinical state or by other modes of therapy administered to the participant.

8 Statistical consideration and data analysis plan

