2.2 SECONDARY OBJECTIVES

The level of concordance between a clinical staff member's opinion and results from the WOUNDCHEK™ detection kit defining the assessment of infection presence in lower limb ulcers.

Evaluate if there are factors associated with infection rates and/or WOUNDCHEK™ result, including clinical indicators of infection such as erythema, purulence, odour, and patient characteristics (health status, co-morbidities, demographic). These include, but are not restricted to:

- Type of wound
- Wound size
- Chronicity of wound
- Clinical indicators of infection, including degree of erythema, purulence, and pain
- Presence of co-morbidities
- Patient health status
- Clinical rater

Assess if there are any trends in bacterial protease detection rates in ulcers when patients are followed up, ie result of first test versus second follow-up test of same ulcer

Evaluate if clinical staff deviate from their initial treatment plan once the WOUNDCHEK result is available to them during a consultation.

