3 INVESTIGATIONAL PLAN

3.1 TRIAL DESIGN AND TIMELINE

The study is a prospective, single-centre, non-randomised, observational design. There is no 'gold standard' accepted detection test for infection available. Clinical guidelines stipulate that clinical judgement concerning the presence or absence of infection is the recommended clinical practice. Samples should only be sent off to a microbiology department to confirm the causative pathogen and inform choice of antibiotics. Therefore, the results of the novel detection infection test kit will be compared with the clinical staff member's judgement of infection status. Table 2 shows the anticipated timeline for the study. Appendix 3 summarises the patient pathway for the study.

For this study, appropriate clinical staff (vascular nurses, practice nurses, tissue viability or podiatry staff) will provide judgements on leg/foot wound infection status. This (ultimately subjective) evaluation can potentially contribute to variability in the detection of infection.

During the study period, all patients can continue to be managed and receive their standard treatment regime by their usual clinical team. Wound dressing selection, dressing frequency and all other aspects of their wound care will continue to be the responsibility of the clinical team. This study will, however, record if the clinical staff member was influenced by the WOUNDCHEK result in terms of dressing choice, antibiotics use, microbiological test swabbing, and interaction with the multidisciplinary team. The latter, MDT, is a group of clinical staff who discuss optimal management of patients with high-risk and more complicated wounds.

Table 3, Anticipated study timeline

Month	Setup	Cohort	Analysis
Nov 2022	Submission to		
	NRES and HRA		
	NIHR portfolio adoption		
Feb 2023	HRA and Trust approval	Start recruitment	
Apr 2024		Finish all recruitment	
Jul 2024		Final visit, last patient	
Aug 2024			Finalise analysis & report

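### Read literally, the causality definitions in Section 7.3 label harm arising through care changed by the test result as not related, and leave some events in neither category

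*Protocol*

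**What the plan says.** Section 7.3 sets the task broadly: "The relationship of each adverse event to the trial must be determined by a medically qualified individual", using the definitions listed beneath that sentence. There are two. The first sets the conditions for calling an event related: "Related: The adverse event follows a reasonable temporal sequence from swabbing. It cannot reasonably be attributed to any other cause". The second names two sources of harm that take an event out of that class, namely the patient's own condition and therapy other than the test, the latter worded as "or by other modes of therapy administered to the participant".

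Other sections make care that responds to the result part of the design:

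- Section 2.2 lists as a secondary objective: "Evaluate if clinical staff deviate from their initial treatment plan once the WOUNDCHEK result is available to them during a consultation".
- Section 3.1 says the study will "record if the clinical staff member was influenced by the WOUNDCHEK result in terms of dressing choice, antibiotics use, microbiological test swabbing", and also contact with the multidisciplinary team.
- Section 5.2 asks staff to note on the report form when the result influenced them. Appendix 1 has a yes/no treatment-deviation item for weeks 0 and 6.
- Section 8.4 will count and describe these deviations, with later patient and wound outcomes.

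The remaining safety text bears on this as follows:

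- Section 7.1 defines an adverse event without regard to relatedness.
- Section 7.2 sends every serious adverse event to the sponsor within one working day and updates the manufacturer periodically. It describes physical exposure narrowly: "The only device to be in contact with the patient is the sterile swab provided by the hospital".
- Section 8.1 treats a patient who has a serious device-related event and is not withdrawn as a serious protocol deviation.

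**The concern.** A point-of-care test whose only contact with the patient is a hospital swab affects the patient mainly through what staff do with the result. Section 1 of the protocol names the consequences of wrong infection calls: inappropriate antibiotics or antimicrobial dressings on one side, late presentation with spreading infection on the other. A causality rule for this study should be able to connect an event to a decision that the study itself recorded as prompted by the test.

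The Section 7.3 wording does not provide for that. It is also internally inconsistent, because the opening sentence asks about the trial while the definitions look only to swabbing and to the exclusion of every other cause. At stake is the meaning of any count of related events, and whether the Section 8.1 rule reaches serious events that came about through use of the result.

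**Working it through.** No arithmetic applies. The check is to run types of event through the two definitions as written.

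**What the definitions require.** *Related* has two cumulative conditions: (i) the event follows swabbing in a plausible time order, and (ii) no other cause is reasonable. *Not Related* has one: the event was probably produced by the clinical state or by other therapy. Neither makes an exception for therapy that the test result started, changed or stopped.

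**Case 1: direct harm from the swab, with no competing explanation.** Condition (i) is met and condition (ii) is met. The label is Related. The rule works here.

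**Case 2: harm from a therapy started or changed because of the result**, for example a reaction to an antibiotic prompted by a positive test. Condition (i) is met, because the event follows swabbing in time. Condition (ii) fails, because the drug is a reasonable cause. The event fits the other-therapy limb of Not Related.

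**Case 3: harm after a planned therapy was dropped or delayed because of the result.** Condition (i) is again met. Condition (ii) fails, because the untreated wound is a reasonable cause. The event fits the clinical-state limb of Not Related.

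**Case 4: an event with a competing cause that is reasonable but not probable.** Condition (ii) fails, so the event is not Related. The probability condition also fails, so it is not Not Related. No category is available. This does not depend on the result having changed care. Section 8.1 lists co-morbidities such as diabetes, peripheral arterial disease and heart failure, so competing causes can be expected in this population.

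**Which words do the excluding.** Not the reference to swabbing: that is a timing condition, and Cases 2 and 3 satisfy it. The exclusion comes from the sole-cause condition together with the two limbs of Not Related.

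**Does the wider opening sentence rescue the rule?** No. The assessor is told to decide according to the definitions, so where the two differ the definitions govern.

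**Where the label is used.** Recording (Sections 7.1 and 8.1) and serious-event reporting (Section 7.2) do not depend on it. Sections 8.3 and 8.4 contain no analysis by relatedness. The one apparent use is the device-related rule in Section 8.1. That term has no definition of its own, and Section 7.3 is the only causality text it could draw on.

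**The case against.** The strongest reply is that little turns on this. Adverse events are recorded regardless of relatedness. A hospital admission for sepsis after a negative test would reach the sponsor within one working day and the manufacturer in its periodic update. Section 8.4 describes deviations caused by the result and what followed, and the report form captures antibiotics, hospitalisation and death. There is no safety objective or endpoint, the kit is CE-marked, and wound care stays with the clinical team. All of that stands, and it limits the point to misclassification.

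A second reply is that the text is ambiguous rather than fixed. It does not say whether therapy prompted by the study test counts as other therapy, and deciding what probably produced an event is a medical judgement. This stands in part: an assessor could reach a sensible answer, but only by reading into the definitions something they do not say. It does not answer the sole-cause condition or Case 4.

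Three stronger readings are tempting and should not be drawn:

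- *A reader might infer that the rule returns practically no related events.* It does not follow. Direct swabbing harms can still qualify, and no figure in the protocol supports a rate.
- *A reader might infer that the study cannot detect harm from acting on the result.* The recording, reporting and deviation description above contradict that.
- *A reader might size the problem from disagreement between test and clinician*, using the earlier kit's 301 agreements in 383 assessments: 383 - 301 = 82, and 82/383 = 21.4%. That figure belongs to a different kit. It does not reconcile with the 55 and 14 swabs reported beside it, which sum to 69. Section 8.4 plans on its own non-matched proportion, printed as both 20% and 0.16. Above all, a discordant result is neither a changed decision nor an adverse event.

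**Conclusion.** The point holds as a labelling defect that should be fixed. Followed as written, Section 7.3 assigns Not Related to events that arise through care the study records as changed by its own test, and it gives no category to events with a reasonable but not probable alternative cause. This rests on a literal reading of the definitions and on the protocol's own expectation that the result will sometimes change care.

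The size cannot be put in numbers: the documents give no adverse-event rate and no expected frequency of result-driven changes. In scope it is small. The primary comparison, kappa, regressions and sample size are untouched, and events are not lost. What suffers is the meaning of any tally of related events and the reach of the Section 8.1 rule.

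**What to change.** Amend Section 7.3, and any event form that carries its wording, so that it agrees with Sections 2.2, 3.1, 5.2 and 8.4:

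1. Record relatedness separately to (a) the swabbing procedure and (b) a management decision entered on the report form as changed because of the WOUNDCHEK result. The treatment-deviation item in Appendix 1 already identifies the decisions for (b).
2. Replace the sole-cause condition in *Related* with a reasonable possibility of a causal link, and define *Not Related* as its complement so that every event has a category.
3. State that care started, changed or withheld because of the result is not other therapy for this purpose.
4. State that the device-related term in Section 8.1 uses this definition.

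The cost is a wording amendment, with no new visits, data items or staff. A few more events will be classed as possibly related, so the count will look slightly less favourable. Item 4 also widens the set of events to which the Section 8.1 withdrawal rule applies, so the sponsor should confirm that this is intended when reconciling the two sections. Part (b) can be only as complete as the deviation item, which is collected at weeks 0 and 6.
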